6. RATIONAL AND BACKGROUND

6.1. Background

Systemic lupus erythematosus (SLE) is an autoimmune disease that can affect a wide range of organ systems, mainly the skin and musculoskeletal system but also the kidney, heart, lungs, and central nervous system. A total of 11 American College of Rheumatology (ACR) criteria have been established for disease classification, with a minimum of 4 criteria indicating SLE disease [Petri, 2005].

In the US, the estimated average of the reported prevalences of SLE is approximately 10 cases per 10,000 persons, representing about 300,000 patients, and the incidence

increased 2.5-fold between 1950 and 1979 [Uramoto, 1999; Somers, 2007; Balluz, 2001; Naleway, 2005; Ward, 2004; Helmick, 2008]. In the European Union, an estimated overall average of the reported prevalences is 4 to 5 cases per 10,000 persons [Alamanos, 2003; Benucci, 2005; Eilertsen, 2006; Gourley, 1997; Govoni, 2006; Gudmundsson, 1990; Hopkinson, 1993; Johnson, 1995; López, 2003; Nightingale, 2007; Nossent, 2001; Piette, 2004; Samanta, 1992; Ståhl-Hallengren, 2000; Voss, 1998]. As many as 4 million people may be affected worldwide.

More patients with lupus are women than men; the female-to-male ratio in the childbearing years has been reported to be as high as 12:1 [Danchenko, 2006]. In women, SLE typically develops between ages 15 and 44 years, and onset is most likely insidious [Danchenko, 2006]. Complications during pregnancy can include lupus flares, worsening or new onset of renal failure, hypertension, preeclampsia, pulmonary embolism, deep vein thrombosis, major infections, bleeding and thrombotic events. Of the 63 women in the Lupus in Minorities; Nature vs. Nurture (LUMINA) cohort who became pregnant during follow-up, 76% developed complications [Andrade, 2006]. Pregnancy remains contraindicated in SLE patients with severe pulmonary hypertension or restrictive lung disease, heart failure, chronic renal failure, previous severe preeclampsia, HELLP (hemolysis, elevated liver enzyme levels and a low platelet count) despite therapy with aspirin and heparin, and in SLE patients with stroke or severe lupus flare within the previous 6 months [Ruiz-Irastorza, 2011]. Complications of lupus pregnancy can be minimized with careful screening and close cooperation across the health care team. Careful attention to the impact of concomitant medications has had a positive impact on the outcome of pregnancies [Ruiz-Irastorza, 2009; Ruiz-Irastorza, 2011].

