7. RESEARCH QUESTION AND OBJECTIVE(S)

The purpose of the Belimumab Pregnancy Exposure Study is to monitor planned and unplanned pregnancies exposed to belimumab and to evaluate the possible teratogenic effect of this medication relative to the primary outcome of major birth defects, the secondary outcome spontaneous abortion (including ectopic and molar pregnancies), stillbirth, elective termination, preterm delivery, and infant outcomes (small for gestational (SGA) age at birth, postnatal growth deficiencies, developmental concerns and serious infections in live born infants to one year of age) and minor birth defect patterns. The overall aim of the study is to determine whether there is a signal for belimumab teratogenicity when compared to the background rate in an unexposed SLE cohort.

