8.3.2. Outcome definitions

Outcome definitions and details are listed in [Table 2](#).

Table 2 Primary and Secondary Outcome Definitions

Outcome	General definition	Denominator	Pregnancy involving multiples	Outcome assessment	Exposure time	Endpoints
Pregnancy Outcome (Primary)						
Major Birth Defect²	Defined and classified using the CDC coding manual [CDC 2017], reported by the mother and validated through the medical record. The CDC coding manual is utilized to classify defects reported through the ongoing population-based Metropolitan Atlanta Congenital Defects Program (MACDP) and is based on agreed-upon criteria by CDC investigators for major birth defects regardless of etiology. Infant medical records are abstracted and reviewed by the study research team leaders.	Pregnancies ending in live births	Included counted as one case if at least one infant has a birth defect.	At birth or prior [may also be detected up to 1 year of age]	3 months prior to LMP and/or first trimester	
Primary analysis (among pregnancies with at least one live births) Cohort 1: At least one malformed infant in an individual pregnancy among pregnancies ending in at least one live birth with exposure to 3 months prior to LMP and/or 1st trimester
 
Cohort 2: At least one malformed infant in an individual pregnancy among pregnancies ending in at least one live birth with no exposure to belimumab any time in pregnancy³
 
Secondary analysis (among all pregnancies excluding lost-to-follow up) Cohort 1: At least one malformed infant or fetus in an individual pregnancy among pregnancies ending in at least one live birth with exposure to belimumab 3 months prior to LMP and/or 1st trimester
 
Cohort 2: At least one malformed infant or fetus in an individual pregnancy among pregnancies ending in at least one live birth with no exposure to belimumab any time in pregnancy³

Outcome	General definition	Denominator	Pregnancy involving multiples	Outcome assessment	Exposure time	Endpoints
Pregnancy Outcomes (Secondary)						

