
Elective Termination
	
Defined as deliberate termination of pregnancy at any time in gestation by surgical or medical means. Reasons for elective abortions are captured and are classified as due to medical reasons or social reasons.
	
Pregnancies
	
Included counted as one case if all multiple pregnancies ended in elective termination. Pregnancy is counted as a live birth outcome if at least one pregnancy resulted in a live-born infant
	
During pregnancy
	
3 months prior to LMP and/or at any time in pregnancy³ prior to outcome
	
Cohort 1: Elective termination among all pregnancies¹ with exposure at any time in pregnancy³; Cohort 2: Elective termination among all pregnancies¹ with no exposure at any time in pregnancy³;

Preterm Delivery
	
Defined as a spontaneous or induced delivery at <37 gestational weeks, reported by the mother and validated through the medical record. Please refer to Section 8.3.1 for further description of the method for defining gestational age and therefore preterm birth.
	
Pregnancies ending in live births
	
Excluded due to inherent higher risk of preterm birth in multiple
	
At birth
	
3 months prior to LMP and/or at any time in pregnancy³ prior to 37 weeks
	
Cohort 1: Preterm delivery among pregnancies enrolled prior to 37 weeks' gestation and ending in at least one live birth, with exposure at any time in pregnancy³ prior to 37 weeks; Cohort 2: Preterm delivery among pregnancies enrolled prior to 37 weeks' gestation and ending in at least one live birth, with no exposure at any time in pregnancy³;

Outcome	General definition	Denominator	Pregnancy involving multiples	Outcome assessment	Exposure time	Endpoints
Infant Outcomes (Secondary)						

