8.3.3. Confounders and effect modifiers

The potential confounders/effect modifiers listed below will be considered in multivariable analyses, where possible, as well as others that are relevant to each of the study outcomes:

- Maternal and paternal age
- Previous pregnancy history: gravidity and parity, previous spontaneous abortions and elective terminations
- Maternal and paternal race/ethnicity, education, occupation, socioeconomic status
- Pre-pregnancy body mass index
- Previous preterm delivery
- Previous child with a birth defect
- Maternal conditions: e.g., depression, diabetes
- Maternal exposures: gestational timing and dose of all over-the-counter and prescription medications, including all medications for the treatment of SLE used during pregnancy; vitamin and mineral supplements, herbal products; illnesses; fever; vaccinations
- Prenatal testing: ultrasound and other prenatal tests; timing in gestation and results
- Pregnancy complications: e.g., pregnancy induced hypertension, gestational diabetes, prolonged labor (definitions included in Section 14 Glossary)
- Maternal lifestyle habits: cigarette smoking, alcohol consumption and illicit drug use
- SLE disease severity assessment (see ANNEX 1 [Section 15.1] for details)
- Relevant lab values where available (e.g., CBC with differential, urinalysis: protein, red blood cell (RBC), white blood cell (WBC), casts, urine protein:creatinine ratio, dsDNA antibody, anti-phospholipids C3 and C4)
- Infant complications: e.g., hospitalizations, congenital heart block,
- Relevant pediatric exposure: any vaccines administered, infections requiring hospitalization in first year of life, breastfeeding status

Methods for identifying and controlling for these confounders and/or effect modifiers are described in Section 8.7.1. The SAP will provide greater detail on the definitions of, the identification of and the controlling for confounders and/or effect modifiers.

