8.7. Data analysis

8.7.1. Essential analysis

A stepwise approach will be used for the analysis: The initial analysis will be descriptive and unadjusted. Where numbers permit, multivariable analyses will be conducted for the primary and secondary analyses to adjust for possible confounders.

Statistical methods:

A detailed SAP will be prepared and finalized prior to the conduct of any study analysis. Patient characteristics will be summarized within each cohort for the interim and final reports.

Table 6 summarizes the exposure window for each outcome.

Table 6 Summary of Exposure Window for Each Outcome

Outcome	Exposure Window
Major Birth Defects	3 months prior to LMP to the end of the 1 st trimester
Minor Birth Defects	3 months prior to LMP to the end of the 1 st trimester
Spontaneous Abortion/Miscarriage	3 months prior to LMP to prior to 20.0 weeks' gestation
Preterm Delivery	3 months prior to LMP to prior to 37.0 weeks' gestation
Other Outcomes	3 months prior to LMP to the end of the pregnancy

For the primary endpoint, the exposure of interest is belimumab exposure in the pre-conception/first trimester period. For this study, this exposure is defined as any dose from 3 months prior to the 1st day of LMP and up to 13 weeks after the 1st day of the LMP. The primary comparison will be on the rate of major birth defects between Cohort 1 and Cohort 2 among pregnancies resulting in at least one live born infant. A point estimate of the crude (i.e. unadjusted) RR of Cohort 1 versus Cohort 2, as well as its 95% confidence intervals (CIs) will be computed.

The comparison will also be carried out within each of two strata, according to whether the woman had prenatal diagnostic testing, such as level II ultrasound, amniocentesis or chorionic villus sampling, prior to enrollment in the study or not.

The same analysis will be repeated using the second numerator and denominator encompassing pregnancies ending in at least one live births, stillbirth, spontaneous abortion or elective termination, but excluding those lost-to-follow-up.

Due to the observational nature of the study, the above crude estimate of RR will be further adjusted for potential confounders, provided that there are sufficient number of events. A complete list of potential confounders will be provided in a separate table for each outcome prior to the final analysis, based on scientific knowledge including literature review. In addition, all of the following three criteria will be applied in

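### Elective terminations are coded only as medical or social and compared as one pooled count, so terminations for a fetal defect are not separated from those for maternal disease and the comparison is not specific for teratogenicity

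*Protocol*

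**What the plan says.** Section 8.3.2, Table 2, elective termination row: "Reasons for elective abortions are captured and are classified as due to medical reasons or social reasons". The glossary (Section 14) repeats this two-way code. The endpoint does not use even that split. For the exposed cohort it is "Elective termination among all pregnancies¹ with exposure at any time in pregnancy³", and the comparator is worded in parallel.

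Section 7 lists elective termination among the secondary outcomes of a study meant "to evaluate the possible teratogenic effect of this medication relative to the primary outcome of major birth defects".

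A separate analysis also bears on terminated pregnancies. Section 8.7.1 repeats the birth-defect comparison on a population "encompassing pregnancies ending in at least one live births, stillbirth, spontaneous abortion or elective termination, but excluding those lost-to-follow-up". Table 2 heads the same analysis as covering all pregnancies except those lost to follow-up, yet words its endpoint as "At least one malformed infant or fetus in an individual pregnancy among pregnancies ending in at least one live birth with exposure to belimumab", with matching wording for the comparators.

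The raw material for a finer code is collected. Section 8.3.3 lists "Prenatal testing: ultrasound and other prenatal tests; timing in gestation and results". Section 8.4 has every participant asked about birth defects once the pregnancy ends, whatever its outcome. Table 3 abstracts major birth defects from LMP onward in both cohorts.

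**The concern.** A termination after a fetal defect is found carries information about teratogenicity. A termination because the mother is too ill carries information about lupus. The plan's medical class holds both, and the Table 2 endpoint adds the social terminations as well.

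Maternal indications are plausible here. Section 6.1 states: "Pregnancy remains contraindicated in SLE patients with severe pulmonary hypertension or restrictive lung disease, heart failure, chronic renal failure". Belimumab is an add-on for active SLE, so exposed women may be sicker. That is an inference, but Section 8.1 makes control of confounding depend on similar severity in the two cohorts, and Section 8.9 concedes that some differences may not be adjustable.

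The primary analysis is also affected. It counts live births only, so a malformed fetus that is terminated leaves it. Section 8.9 says the relative risk stays unbiased if defects missed in this way are missing at random with respect to exposure. The number of fetal-indication terminations in each cohort is a direct check on that condition, and the medical/social code does not supply it. Such cases can arise during follow-up: Section 8.2.1 excludes women whose fetus already has a diagnosed major structural defect, and Section 8.5 expects enrollment at 7–10 weeks post-LMP on average, so later diagnoses occur within the study.

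**Working it through.** **Plan figures.** The protocol gives no power or detectable effect for elective termination, so there is no stated figure to reproduce. The nearest one is for spontaneous abortion in Section 8.5: 200 × (1 − 0.05 − 0.05) = 180, which agrees. With 180 per cohort and a 10% background rate, the minimum detectable ratio is 2.06, against the stated 2.1.

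**Can the coding tell two explanations apart?** The input from the protocol is a 5% elective abortion rate (Section 8.5) on 200 women, that is 10 terminations. The split of those 10 and both exposed scenarios are assumptions, chosen to show that the coding can hide the difference.

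| | Fetal defect | Maternal | Social | Medical (fetal + maternal) | All |
|---|---|---|---|---|---|
| Comparators | 2 | 2 | 6 | 4 | 10 |
| Exposed A: sicker mothers, no teratogenicity | 2 | 6 | 6 | 8 | 14 |
| Exposed B: teratogenic, same severity | 6 | 2 | 6 | 8 | 14 |

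- Pooled ratio: 14/10 = 1.4 in A and in B.
- Medical ratio: 8/4 = 2.0 in A and in B.
- Fetal-defect ratio: 2/2 = 1.0 in A, 6/2 = 3.0 in B.

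**How far does pooling dilute a signal?** Let *s* be the share of comparator terminations that are for a fetal defect, and *R* the ratio for that component alone. Then pooled RR = (1 − *s*) + *sR*. The protocol does not give *s*, so a range of 5% to 40% is shown, with *R* = 3. Power uses the two-sided 0.05 normal approximation for two proportions, with 190 per cohort (200 less 5% lost) and a 5% rate, so 190 × 0.05 = 9.5 terminations are expected among comparators.

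| *s* | Expected fetal-defect terminations, comparator vs exposed | Pooled RR | Power, pooled | Power, fetal-defect class alone |
|---|---|---|---|---|
| 5% | 0.5 vs 1.4 | 1.10 | 4% | 10% |
| 10% | 1.0 vs 2.9 | 1.20 | 6% | 16% |
| 20% | 1.9 vs 5.7 | 1.40 | 13% | 29% |
| 40% | 3.8 vs 11.4 | 1.80 | 33% | 51% |

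The approximation is unreliable at such counts, so these powers are orders of magnitude only. For reference, the pooled endpoint reaches 80% power only at an RR of about 2.65. Over assumed background rates of 2% to 8%, that becomes 4.17 to 2.20.

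**Does the secondary birth-defect analysis catch these cases?** Three statements have to be read together:

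1. Section 8.7.1 puts elective terminations in the population.
2. Table 2 heads the analysis in the same sense, but its endpoint text requires at least one live birth. Read literally, a terminated singleton with a malformation is not counted.
3. Section 8.7.1, on right censoring, places terminations without fetal autopsy among pregnancies with unknown outcomes. A termination for a suspected defect that was never confirmed may therefore not be counted as a defect. Its recorded reason could be the main trace left, and the code files it as medical.

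**The case against.** The strongest reply is that nothing is lost. Reasons are captured before they are classed, defects are asked about after every pregnancy, prenatal results are collected, and defects are abstracted from LMP. A reader might infer from the two-way code that fetal and maternal terminations can never be told apart. The documents do not support that: the split can be derived from data already held.

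A reader might also infer that the study has no route to a teratogenic signal from terminated pregnancies. Section 8.7.1 plans one. Table 2's live-birth wording cannot be taken as the settled plan, because it conflicts with its own heading and with Section 8.7.1. Equally, Section 8.7.1 cannot be assumed to prevail until the two are reconciled.

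It can further be said that no section makes elective termination a stand-alone test of teratogenicity, that severity is a listed confounder with endpoint-specific propensity scores planned where numbers permit, and that table shells are left to the SAP. All of this is true. But the two-level code is a stated definition, given twice, and not a gap left open. With about 10 terminations per cohort, adjustment may not be feasible.

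Finally, splitting does not bring power. In scenario B, 6/200 against 2/200 gives a two-sided Fisher p of 0.28. That stands, and it limits what the fix can promise.

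**Conclusion.** The point holds as a defect of coding and reporting. Under the plan's code, fetal-defect terminations are not separated from maternal ones, and the pooled comparison is not specific for teratogenicity. A three-fold rise confined to fetal-defect terminations would appear as a pooled RR of only 1.10 to 1.80, for assumed shares of 5% to 40%. The 5% rate and cohort size come from the protocol; the shares, the three-fold rise, the 2/2/6 split and both exposed scenarios are assumptions. No figure stated in the protocol is wrong.

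The conflict between Table 2 and Section 8.7.1 rests on the text alone and needs no assumption. It matters because the secondary birth-defect analysis is the main planned route by which defects in terminated pregnancies would be counted.

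**What to change.** 1. In Table 2 and the glossary, divide the medical class into fetal defect (suspected or confirmed) and maternal medical reason, and keep social reasons as the third class.
2. Tabulate terminations by reason and cohort, descriptively, and keep the pooled rate beside them.
3. Cross-list the fetal-defect class with the major birth defect listings. Use its counts by cohort to examine the condition in Section 8.9 that missed defects are random with respect to exposure.
4. Reconcile the Table 2 secondary birth-defect endpoint with its heading and with Section 8.7.1, so that malformed fetuses in terminated pregnancies are counted.

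The cost is one more coding level on information already collected, one more table and a wording correction. Counts per class will be very small and intervals wide, so the table should be read case by case and not as a test.

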8.3. Variables

8.3.1. Exposure definitions

Belimumab-exposed cohort: Exposure is defined as any dose of belimumab for any length of time from 3 months prior to the first day of the LMP (i.e., a period of approximately 5 belimumab terminal half-lives) through the end of pregnancy, as reported by the mother and validated through medical record review (mean termination elimination half-life of 8.5 to 14.1 days, [Furie, 2008]). Belimumab exposure will be further categorized by earliest trimester of exposure (definition from <https://www.womenshealth.gov/pregnancy/youre-pregnant-now-what/stages-pregnancy>; <https://www.ucsfhealth.org/conditions/pregnancy/trimesters>). For this study, pre-conception exposure is defined as between 3 months prior to LMP to the first day of the LMP, first trimester exposure is defined as any dose from 1st day of LMP and up to 13 weeks after 1st day of LMP; second trimester is defined as >13 weeks through 26 weeks

after 1st day of LMP, and third trimester is defined as >26 weeks after 1st day of LMP. Details of varying levels of exposure and timing will be included in the Statistical Analysis Plan (SAP).

When evaluating the primary outcome of major birth defects, exposure will be defined as yes/no in either the preconception and/or first trimester of pregnancy for major birth defects as the primary outcome. However, exposure to belimumab in the second (>13 weeks through 26 weeks after 1st day of LMP) and third trimester (>26 weeks after 1st day of LMP), will be considered for those selected major birth defects that are potentially biologically plausibly related to later pregnancy exposures, e.g., craniosynostosis [Jones, 2013]. For spontaneous abortion, the exposure is defined as yes/no in the 3 months prior to LMP and/or any time in pregnancy prior to 20 weeks of gestation, for preterm delivery, the exposure is defined as yes/no in the 3 months prior to LMP and/or any time in pregnancy prior to 37 weeks, for minor birth defects, the exposure is defined as yes/no from 3 months prior to LMP through the end of the first trimester, and for the other secondary outcomes, exposure is defined as yes/no anytime in pregnancy (from 3 months prior to LMP [as defined in Section 8.3.2] to pregnancy outcome).

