Minor birth defect pattern	A minor birth defect is defined as a defect that has neither cosmetic nor functional significance to the child and as itemized on the study-related dysmorphology examination form (Jones, 2013). Minor defect pattern will be defined using the following two steps: 1) identify infants with at least 3 minor structural defects of any type in the belimumab-exposed group and 2) from among infants with at least 3 minor structural defects in the belimumab-exposed group, identify any 2 or more unrelated infants with the same 3 specific minor structural defects. The prevalence of each specific pattern or patterns, if any, that are identified in the belimumab-exposed infants will be identified in the unexposed SLE comparator group. As an example, if 2 infants in Cohort 1 had the following	Live born infants	Included each counted separately for definition 1 However, in the analysis of the second definition, only one infant from a twin or higher order multiple pregnancy can be qualified as a child with the same pattern of minor structural defects, due to lack of independence for this outcome between related individuals.	Any time after birth	3 months prior to LMP and/or anytime in the 1 st trimester	1) Infant with at least 3 minor defects of any type: Cohort 1: Infants ≥ 3 minor birth defects of any type identified up to among live born infants who received a dysmorphological examination, with exposure at any time in pregnancy ³ Cohort 2: Infants ≥ 3 minor birth defects of any type identified up to among live born infants who received a dysmorphological examination, with no exposure at any time in pregnancy ³ ; 2) Infants with the same 3 minor defect patterns: Cohort 1: Infants with the same pattern of 3 minor defects identified up to among live born infants with ≥ 3 minor birth defects of any type identified any time in pregnancy ³ ; Cohort 2: Infants with the same pattern of 3 minor defects identified up to among live born

Outcome	General definition	Denominator	Pregnancy involving multiples	Outcome assessment	Exposure time	Endpoints

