	
minor structural defects: "hair pattern unruly", "prominent nasal bridge", and "clinodactyly 5th finger bilateral", this would constitute one specific pattern of minor structural defects. For each specific pattern identified in Cohort 1, infants in Cohorts 2 who have the same specific pattern(s) are selected to comprise the numerator for those cohorts. In infants who have more than one specific patterns of at least 3 minor structural defects, each specific pattern will qualify as its own endpoint; therefore, the infant would be counted more than once.
					
infants, with ≥ 3 minor birth defects of any type identified, with no exposure at any time in pregnancy³;

Post-natal growth deficiency
	
Defined as postnatal size at approximately 1 year of age (weight, length or head circumference) less than or equal to the 10th percentile for sex and age using National Center for Health Statistics (NCHS) pediatric growth curves, and adjusted postnatal age for premature infants if the postnatal measurement is obtained at less than 1 year of age. [CDC, 2000].
	
Live born infants
	
Excluded due to inherent higher risk of reduced birth size in multiple
	
From birth up to 1 year of age
	
3months prior to LMP and/or at any time in pregnancy³
	
Cohort 1: Post-natal growth deficiency identified up to 1 year of age among live born infants with exposure at any time in pregnancy³
 
Cohort 2: Post-natal growth deficiency identified up to 1 year of age among live born infants, with no exposure at any time in pregnancy³

Developmental concerns
	
Defined as an abnormal score within the scoring guidelines of the Ages and Stages Questionnaire (ASQ) (Squires, 2009). The ASQ is administered at 12 months of age as a screening tool for developmental milestones by parent report. The ASQ-3 will be sent electronically to the participant or, if the participant prefers, a hard copy questionnaire will be mailed for completion.
	
Live born infants
	
Included each counted separately
	
At 1 year of age
	
3months prior to LMP and/or at any time in pregnancy³
	
Cohort 1:Developmental concerns identified at 1 year of age among live born infants, with pregnancy exposure at any time in pregnancy³;
 
Cohort 2: Developmental concerns identified at 1 year of age among live born infants, with no exposure at any time in pregnancy³

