Endpoints relevant to SGA at birth and postnatal growth deficiency at about 1 year of age in weight, height and head circumference (excluding multiple births) are all binary endpoints. The analysis of each of these outcomes will be similar to the analysis of the primary outcome.

Multiple births will be included in the analyses of minor structural defects, developmental concerns and serious infections. The outcome variables thus contain likely correlated data, and the generalized estimating equations (GEE) approach will be used to estimate the crude RR with 95% CI. The causal effect will be estimated similar to the primary outcome, but in place of logistic regression it will be GEE with the logistic link function. The CIs are obtained by 10,000 bootstraps, where the mothers (not infants) will be resampled with replacement.

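### Minor-defect patterns (definition 2) are selected because exposed infants share them and then compared with Cohort 2 on the same data, so the RR is biased above 1 for rare patterns

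*Protocol*

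**What the plan says.** Protocol Table 2 (section 8.3.2, repeated in the section 14 glossary) gives the minor-defect endpoint two definitions.

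- **Definition 1** is an infant with three or more minor defects of any type. Both cohorts get a numerator.
- **Definition 2** is a specific three-defect pattern. Step 1 is to "identify infants with at least 3 minor structural defects of any type in the belimumab-exposed group". Step 2 is, "from among infants with at least 3 minor structural defects in the belimumab-exposed group, identify any 2 or more unrelated infants" sharing the same three defects. Cohort 2 enters afterwards: "For each specific pattern identified in Cohort 1, infants in Cohorts 2 who have the same specific pattern(s) are selected to comprise the numerator". Where an infant has several patterns, "each specific pattern will qualify as its own endpoint; therefore, the infant would be counted more than once". No search for patterns that recur in Cohort 2 is described.

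Section 8.7.1 gives the analysis. "Multiple births will be included in the analyses of minor structural defects, developmental concerns and serious infections", and for these outcomes "the generalized estimating equations (GEE) approach will be used to estimate the crude RR with 95% CI", followed by a causal estimate with bootstrap intervals. The two definitions are not separated.

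On exposure, section 8.3.1 says: "for minor birth defects, the exposure is defined as yes/no from 3 months prior to LMP through the end of the first trimester". Table 6 and the Exposure time column of the Table 2 row agree. The Endpoints cell of that row instead takes Cohort 1 infants "who received a dysmorphological examination, with exposure at any time in pregnancy", a term that footnote 3 extends to the end of pregnancy.

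On the denominator, the Table 2 column gives live born infants. The Endpoints cell gives examined live born infants for definition 1, and live born infants who already have three or more minor defects for definition 2.

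**The concern.** Under definition 2, one arm's data decide which comparison is made, and the same data then supply that arm's numerator. The exposed count cannot fall below 2, and the comparator count has no such floor. An ordinary RR and CI ignore that condition, so for a rare pattern the estimate tends to lie above 1 even if belimumab has no effect. The study's stated aim is to detect a teratogenic signal, so an error in that direction matters.

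The two wording conflicts add to this. Cohort 1 admits exposure at any time up to the end of pregnancy. Infants first exposed after the first trimester are therefore counted under the Endpoints cell but not under section 8.3.1. A denominator of infants who already have three or more defects conditions on an outcome, and gives a share among affected infants instead of the prevalence that the definition promises.

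**Working it through.** **No figure to reproduce.** The protocol gives no rate, power or RR for this endpoint. The cohort sizes do reproduce from section 8.5: 200 × 0.85 = 170 and 200 × 0.80 = 160 pregnancies with a live birth per cohort.

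**Inputs.**
- n = 170 per cohort (section 8.5), standing in for examined infants. Section 8.9 says examinations may be incomplete and gives no proportion, so n = 160 and n = 100 are also shown.
- Selection rule: at least 2 exposed infants (Table 2).
- q, the prevalence of one specific pattern, is not in the protocol. Assumed 0.05% to 5%, equal in both cohorts (true RR = 1). For scale, three independent defects of 10% each coincide in 0.1³ = 0.1% of infants, and three of 20% each in 0.2³ = 0.8%.

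**Model.** X1 and X2 are independent Bin(n, q), conditional on X1 ≥ 2, with equal denominators.
- P(selected) = 1 − (1−q)^n − nq(1−q)^(n−1)
- E(X1 | selected) = nq[1 − (1−q)^(n−1)] / P(selected)
- E(X2) = nq, and P(X2 = 0) = (1−q)^n

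**Worked line, q = 0.2%, n = 170.** nq = 0.34, (0.998)^169 = 0.7129 and (0.998)^170 = 0.7115. P(selected) = 1 − 0.7115 − 0.34 × 0.7129 = 0.046. E(X1 | selected) = 0.34 × 0.2871 / 0.0461 = 2.12, against E(X2) = 0.34, a ratio of 6.2 where the truth is 1.

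**Results, n = 170, given that the pattern was selected.**

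| q | P(RR>1) | P(RR<1) | Ratio of expected counts | P(no Cohort 2 case) |
|---|---|---|---|---|
| 0.05% | 0.997 | 0.000 | 23.9 | 0.92 |
| 0.1% | 0.988 | 0.001 | 12.1 | 0.84 |
| 0.2% | 0.958 | 0.005 | 6.2 | 0.71 |
| 0.5% | 0.833 | 0.043 | 2.7 | 0.43 |
| 0.8% | 0.714 | 0.109 | 1.9 | 0.26 |
| 1% | 0.650 | 0.158 | 1.6 | 0.18 |
| 2% | 0.488 | 0.344 | 1.1 | 0.03 |
| 5% | 0.451 | 0.449 | 1.0 | 0.00 |

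The remaining probability is RR = 1. At q = 0.2%, P(RR>1) is 0.963 for n = 160 and 0.984 for n = 100. With no Cohort 2 case the RR is not finite.

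**Symmetric search, n = 170, q = 0.2%.** If a pattern qualifies when 2 or more infants share it in either cohort, P(RR>1) = P(RR<1) = 0.491. If it qualifies on 2 or more infants in the pooled cohorts, both are 0.297. In each case the ratio of expected counts is 1.00. The direction of the bias therefore comes from the one-sided search.

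**Significance of a typical result.** For 2 v 0 at n = 170, the exact two-sided p is 2 × (170 × 169)/(340 × 339) = 0.50.

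**The case against.** The strongest reply is that no sentence assigns an RR to each pattern. Table 2 can be read as a look-up of exposed-derived patterns in the comparator group. The reason section 8.7.1 gives for GEE, correlated siblings, fits definition 1, because definition 2 allows only one infant per multiple pregnancy. Section 8.5 also presents the study as signal detection, and looking for a recurrent phenotype among exposed infants suits that purpose. This stands as far as it goes: the search is legitimate if reported descriptively. But section 8.7.1 covers minor structural defects without separating the definitions, and no other method is given for definition 2.

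Three stronger readings are tempting, and the documents do not support them.

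- *The whole minor-defect endpoint is biased.* Definition 1 is counted in both cohorts and is not selected on exposed data.
- *The conditional denominator hides a rise in infants with multiple defects.* Definition 1 measures that rise directly, among examined infants.
- *The plan will produce statistically significant false signals.* No hypothesis test is named, and a typical 2 v 0 result has p = 0.50. What is shown is a biased or inestimable ratio. How often an interval would exclude 1 was not calculated.

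On the window, the Endpoints cell is the outlier against three consistent places, and definition 2's Cohort 1 text is garbled as read. This is a reconciliation of wording. The Cohort 2 requirement of no exposure at any time matches the primary outcome's comparator and is not a conflict.

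**Conclusion.** The point holds for definition 2 only. If the RR of section 8.7.1 is computed for patterns chosen as Table 2 prescribes, it is biased above 1 for rare patterns: the null P(RR>1) falls from about 0.99 to 0.65 as pattern prevalence rises from 0.1% to 1% with 170 infants per cohort. It is also often not estimable. At 2% the bias is small (ratio of expected counts 1.1), and at 5% it has gone. The size rests on assumed pattern prevalences, equal denominators and the number of infants examined, none of which the protocol gives for this endpoint. The direction for rare patterns follows from the selection rule.

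Separately, the Endpoints cell contradicts its own row, section 8.3.1 and Table 6 on the exposure window, and contradicts the Denominator column on who is counted. Both need correcting. For a secondary endpoint this is a change that should be made, and it does not threaten the primary analysis.

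**What to change.** 1. For definition 2, choose one of two routes. Either report exposed-derived patterns descriptively, with counts in both cohorts and no RR or CI, and say so in section 8.7.1. Or identify recurrent patterns symmetrically before any comparison, in the pooled infants with exposure masked or by the same two steps in each cohort. Pooling has one advantage: selection then depends only on the total count and not on how it splits between cohorts.
2. Use live born infants who had the dysmorphology examination as the denominator for both definitions, in the Denominator column and the Endpoints cell.
3. Align the Cohort 1 text of the Endpoints cell with the Exposure time column, section 8.3.1 and Table 6: 3 months before LMP through the end of the first trimester. The Cohort 2 wording can stay.
4. Carry the changed pattern definition into the glossary.

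The cost is rewording and a different tabulation of data already collected. No further examinations or participants are needed.
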